7. RATIONALE AND BACKGROUND

Lomitapide, a microsomal triglyceride transfer protein (MTP) inhibitor, was approved as Juxtapid[®] in the United States on 21Dec2012 and was authorized as Lojuxta[®] in the European Union on 31Jul2013. The approved indications in the two regions are quite similar and are included in the table below:

REGION	APPROVED INDICATION
EU	Indicated as an adjunct to a low-fat diet and other lipid-lowering medicinal products with or without low density lipoprotein (LDL) apheresis in adult patients with homozygous familial hypercholesterolaemia (HoFH).
	Genetic confirmation of HoFH should be obtained whenever possible. Other forms of primary hyperlipoproteinemia and secondary causes of hypercholesterolemia (e.g., nephrotic syndrome, hypothyroidism) must be excluded.
US	Indicated as an adjunct to a low-fat diet and other lipid-lowering treatments, including LDL apheresis where available, to reduce low-density lipoprotein cholesterol (LDL-C), total cholesterol (TC), apolipoprotein B (apo B), and non-high-density lipoprotein cholesterol (non-HDL-C) in patients with homozygous familial hypercholesterolemia (HoFH).
	Limitations of Use: The safety and effectiveness of JUXTAPID have not been established in patients with hypercholesterolemia who do not have HoFH. The effect of JUXTAPID on cardiovascular morbidity and mortality has not been determined.

HoFH is a serious, life-threatening disease caused by mutations in both alleles that encode the low-density lipoprotein receptor (LDL-R), or proteins known to affect LDL receptor functionality. Subjects with HoFH typically have 4-10 fold elevations in low-density lipoprotein cholesterol (LDL-C) and develop premature atherosclerosis and coronary heart disease and can have cardiovascular events and complications such as myocardial infarctions or aortic stenosis in the first decade of life. Untreated, subjects generally do not survive past age 30 (Raal, et al. 2011). Due to its rarity and early mortality, the prevalence of HoFH is not well characterised. No studies accurately quantify the prevalence or incidence of the disease. The frequency of HoFH has been calculated to be 1 in 1 million in the general population based upon the estimated prevalence of the heterozygous state (1 in 500). In geographic regions with a presumed founder effect the prevalence has been observed to increase up to 10 in 1 million (Goldstein, et al., 1973; Goldstein, et al., 2001). Women of reproductive age are among those affected by HoFH.

Pregnancy is an ESI in women exposed to lomitapide for 2 reasons. First, there are no reliable data on the use of lomitapide in pregnant women. Lomitapide may cause foetal harm when administered to a pregnant woman based on findings of teratogenicity in animal studies.

Confidential Page 18 of 54

Lomitapide was teratogenic in rats in the absence of maternal toxicity at an exposure (AUC) estimated to be less than that in humans at 60 mg. There was no evidence of embryofoetal toxicity in rabbits at 3 times the maximum recommended human dose (MRHD) of 60 mg based on body surface area. Embryofoetal toxicity was observed in rabbits in the absence of maternal toxicity at \geq 6.5 times the MRHD. In ferrets, lomitapide Aegerion was both maternally toxic and teratogenic at <1 times the MRHD.

Second, lomitapide may induce diarrhoea and vomiting due to its mechanism of action and decrease the absorption of oral contraceptives, thereby increasing the risk of unintended pregnancy. Lomitapide MTP inhibition causes triglyceride accumulation not only in the liver but also in the intestine. Presumably, diarrhoea develops as a consequence of this mechanism of action (Samaha et al., 2008). The reduced bowel transit time may affect the absorption of concomitant oral contraceptives.

The lomitapide US Prescribing Information (PI) and the EU Summary of Product Characteristics (SPC) include a contraindication for use during pregnancy and instructions that females of reproductive potential should have a negative pregnancy test before starting lomitapide and use effective contraception during therapy with lomitapide.

The PER will be conducted in all countries that are included in the Lomitapide Observational Worldwide Evaluation Registry (LOWER), Protocol AEGR-733-025. Information on any spontaneous or literature reports of pregnancies with lomitapide exposure from patients who are not enrolled in the PER will be added to the PER analyses once the pregnancies have been followed to outcome by the Aegerion Safety Department or its designee.

The PER will collect data on any pregnancies that occur in women exposed to lomitapide in the 30 days prior to conception or during pregnancy. Due to the rarity of HoFH and the contraindications for lomitapide use during pregnancy, it is anticipated that the PER will collect few pregnancies; however, all eligible pregnancies, whether retrospective or prospective, will be enroled. The pregnancies that are recorded in and reported from the PER will provide valuable information on birth outcomes following exposure to lomitapide. While the outcomes of primary interest are major congenital anomalies, full descriptions of all pregnancies, birth outcomes, and loss-to-follow-up will be provided in the planned annuals reports; the descriptions will include birth weight, gestational age, whether the delivery was a multiple birth, and age at diagnosis of any paediatric abnormalities.

Confidential Page 19 of 54

8. RESEARCH QUESTION AND OBJECTIVES

The PER will evaluate the outcomes of pregnancy in women treated with lomitapide at any time within 30 days prior to first day of Last Menstrual Period (LMP) or during pregnancy. The outcomes of primary interest are major congenital anomalies.

9. RESEARCH METHODS

9.1 Study Design

This PER is a global, longitudinal, observational cohort study of women who were exposed to lomitapide at any time within 30 days prior to the first day of their LMP or during pregnancy. The outcomes of primary interest are major congenital anomalies. The PER will include pregnancies identified from any country where LOWER is conducted. Information on spontaneous and literature reports of pregnancies with lomitapide exposure from patients who are not enrolled in the PER will be added to the PER analyses once the pregnancies have been followed to outcome by the Aegerion Safety Department or its designee. Information on any spontaneous reports of birth defects or literature reports of birth defects that are identified while the PER is open will also be included in the PER analyses.

No study medication will be provided as part of this long term, observational study. The treating physician will make all treatment decisions according to his or her usual practices and will provide prescriptions for his or her patients, as appropriate. The only addition to usual practice is the collection and structured documentation of data from the patient and/or her HCPs. There are no protocol mandated procedures or diagnostic tests.

CC personnel will obtain information from HCPs and/or eligible patients and record data in an EDC system. Data sources for the international study will include HCPs (e.g., gynaecologists, obstetricians, paediatricians, midwives, and primary care practitioners) and patients in countries where direct contact with patients is permitted, such as in the US. Data will be collected at patient enrolment, each trimester, at 6-7 months of gestation, within 4 weeks after the estimated date of delivery (EDD), and for paediatric follow-up at 12 weeks and 12 months of age.

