9.2.4 Prospective and Retrospective Pregnancy Definitions

In order to reduce the bias that may occur when outcome information is known prior to enrolment, eligible women are advised to enrol in the PER as soon as their pregnancy is known, preferably in the first trimester before the condition of the foetus has been assessed through prenatal testing. In order to determine the impact of such a bias, pregnancy reports and outcomes will be classified as either prospective or retrospective and will be analysed separately.

Confidential Page 21 of 54

The criteria for prospective pregnancies are:

Prospective pregnancies will include patients who are enrolled after exposure to lomitapide but before the outcome of the pregnancy is known. An exception will be made that women who have undergone prenatal testing that could provide knowledge of the outcome of pregnancy will be considered as a prospective report if the outcome of the testing is normal.

Note: Because early prenatal testing is so prevalent, it may be difficult to achieve adequate numbers of prospectively identified patients if all pregnancies with prior prenatal testing are excluded from the prospective analysis. Therefore, the primary analysis includes pregnant women enroled prior to outcome but after a prenatal test as long as the test does not indicate an abnormality. However, this practice could potentially bias the results by lowering the overall risks of birth defects. To examine this possible source of bias, the analysis will also be conducted excluding the subgroup of women who reported negative prenatal testing at the time of enrolment.

All other patients will be counted as retrospective pregnancies.

The retrospective and prospective pregnancies will be collected in a similar fashion, but treated separately as part of any analyses or reports.

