9.5 Study Size

HoFH is an ultra-rare disease. The prevalence of defects in both alleles of the LDL-R (homozygous) has been calculated to occur in ∼1 in 1 million persons based on the estimated prevalence of 1 in 500 for the more common heterozygous FH, which is characterised by less severe hypercholesterolaemia.

Every attempt will be made to recruit eligible participants to this PER using methods found to be effective in similar pregnancy exposure registries. However, the number of women who will be candidates for inclusion with an eligible pregnancy cannot be accurately estimated.

Any pregnancies reported in previous clinical studies with HoFH or spontaneous or literature reports of pregnancies with known outcomes will be considered retrospective reports and will be included in the PER and analyzed separately. Any prospective pregnancies reported spontaneously (i.e., from patients not enrolled in the PER) will be handled by the Aegerion Safety Department or its designee. These reports will be included in a pooled analysis of all reports.

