9.7 Data Analysis

Complete analytical specifications, including tables and listings, will be included in the Statistical Analysis Plan (SAP), which will be prepared separately. All statistical analyses will be coordinated by Aggerion or designee.

Confidential Page 34 of 54

Data will be presented for all patients enroled in the PER. An analysis of all PER participants combined will be provided. Separate analyses will also be conducted for prospective and retrospective reports. All data will be pooled for an additional analysis that includes spontaneous and literature reports from patients not participating in the PER. The proportion of pregnancies and births that have been lost to follow-up will also be calculated and reported. The primary outcome is major congenital abnormalities. Data will be presented using descriptive statistics using number and percent for categorical endpoints, n, mean, standard deviation (SD), standard error (SE) of mean, median, minimum (min), maximum (max) for continuous endpoints. The primary analyses will also present 95% confidence intervals (CI). Details of the analysis and table shells will be included in the SAP.

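### Section 9.7.2 does not limit the primary birth-defect rate and its external comparison to prospective pregnancies, and Sections 4.9, 9.1, 9.2.4, 9.5 and 9.7 conflict on which reports may be combined

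*Protocol*

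**What the plan says.** The protocol deals with report types in six places.

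- **Section 9.2.4** classifies pregnancies by whether the outcome was known at enrolment, in order to deal with the bias that such knowledge brings. It then rules: "The retrospective and prospective pregnancies will be collected in a similar fashion, but treated separately as part of any analyses or reports". Its note on prenatal testing describes the primary analysis in terms of women enrolled before outcome, which implies a prospective primary set.
- **Section 9.7** (and the abstract, Section 4.9): "An analysis of all PER participants combined will be provided". Next: "Separate analyses will also be conducted for prospective and retrospective reports". Then: "All data will be pooled for an additional analysis that includes spontaneous and literature reports from patients not participating in the PER".
- **Section 9.1** says, of the registry's analyses in general, that "spontaneous reports of birth defects or literature reports of birth defects that are identified while the PER is open will also be included". It does not say which analyses.
- **Section 9.5** says that pregnancies from earlier HoFH studies, and spontaneous or literature reports with known outcome, "will be considered retrospective reports and will be included in the PER and analyzed separately". Of prospective spontaneous reports from women who are not enrolled it says: "These reports will be included in a pooled analysis of all reports".
- **Section 9.7.2** defines the primary rate as birth defects reported to the PER over live births, with affected losses from 20 weeks added to the numerator. The chi-square test compares the proportion in the PER with external rates. Neither sentence is limited to prospective reports.

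**The concern.** A report that reaches the sponsor because a child had a defect brings an affected case without the unaffected exposed pregnancies that would belong beside it. A proportion containing such reports does not estimate incidence. A confidence interval around it, or a comparison with MACDP, has no valid interpretation. The direction of the error is upward.

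The separation rule in Section 9.2.4 exists to prevent this. The combined and pooled analyses cannot stand with that rule as worded, and the primary formula does not repeat it. The primary safety estimate therefore rests on an implication in one section, while other sections leave room for a different reading. The protocol expects few pregnancies (Section 7), so one or two reports could decide the figure.

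**Working it through.** **Which reports can reach the primary rate**

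1. Sections 4.8 and 7 take pregnancies of both types into the registry, so being in the PER does not mean being prospective.
2. Section 9.5 puts known-outcome spontaneous and literature reports inside the PER, as retrospective reports analysed separately. Section 9.7 describes spontaneous and literature reports as coming from non-participants.
3. Section 9.1 adds spontaneous and literature reports of defects to the PER analyses without limit.
4. Section 9.7.2 counts what is reported to, or observed in, the PER.

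Taken literally, steps 1 to 4 let an outcome-selected report into the primary numerator. If the note in Section 9.2.4 and the second half of the Section 9.5 sentence are carried into Section 9.7.2, it stays out. Section 9.7.2 does not say which applies.

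**How much a few such reports would matter**

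The protocol gives no sample size and no background rate, so there is no figure to reproduce. The following is an illustration. All its inputs are assumptions:

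- n = unselected live births, 10 to 100
- p0 = true and reference rate, 3% (range 2% to 5%)
- k = added reports that exist because of a defect, each taken as a live birth

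Expected proportion = (n × p0 + k) / (n + k).

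For n = 20, p0 = 3%, k = 2: (0.6 + 2) / 22 = 11.8%, or 3.9 times the true rate.

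| n (p0 = 3%) | k = 0 | k = 1 | k = 2 | k = 3 |
|---|---|---|---|---|
| 10 | 3.0% | 11.8% | 19.2% | 25.4% |
| 20 | 3.0% | 7.6% | 11.8% | 15.7% |
| 50 | 3.0% | 4.9% | 6.7% | 8.5% |
| 100 | 3.0% | 4.0% | 4.9% | 5.8% |

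With n = 20 and k = 2, other true rates give:

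- p0 = 2%: 2.4 / 22 = 10.9%, 5.5 times the true rate
- p0 = 5%: 3.0 / 22 = 13.6%, 2.7 times the true rate

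If the two added cases were losses from 20 weeks, Section 9.7.2 would add them to the numerator only, giving 2.6 / 20 = 13.0%.

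**If the chi-square of Section 9.7.2 were applied to such a set**

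Take n = 20, a fixed reference of 3%, and the upper side of a two-sided 5% test. For k = 0 to 3 the test signals at 3 or more affected in total, so the unselected births need only 3 − k. With X binomial(20, 0.03), the chance of a false signal is:

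- k = 0: P(X ≥ 3) = 0.02
- k = 1: P(X ≥ 2) = 0.12
- k = 2: P(X ≥ 1) = 0.46
- k = 3: 1.00

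The chi-square is a poor test at this size. An exact binomial test at one-sided 2.5% gives 0.02, 0.12, 0.12 and 0.46. The inflation remains, but part of the chi-square result belongs to the test.

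**The case against.** The strongest defence is that the protocol already holds the right analysis. Section 9.2.4 implies a prospective primary set and no other section names a different one, so Section 9.7.2 is silent rather than contrary. Section 9.5 keeps known-outcome spontaneous and literature reports for separate analysis. Section 9.7 calls the pool additional and also plans separate prospective and retrospective analyses. Details and table shells are left to an SAP that is not at hand.

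Much of this stands, and it rules out several stronger readings that a reader might infer:

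- **That the primary rate is contaminated, or that the pool is primary.** The documents do not say so. They fail to exclude it.
- **That the pool gets a confidence interval and a test against MACDP.** Section 9.7 attaches intervals to the primary analyses, and Section 9.7.2 tests the proportion in the PER. Nothing assigns either to the full pool.
- **That prospective spontaneous reports are usable only in the mixed pool.** Section 9.3.4.1.2 lists pregnancies reported directly to the sponsor as a source of participants. Only those who do not enrol go to the pool.
- **That collating all reports is meaningless.** In an ultra-rare disease, counts and case descriptions by source serve signal detection. Only the pooled proportion, read as an incidence, has no valid meaning.

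What the defence does not remove is the literal conflict between a rule covering every analysis and two planned combinations, the disagreement between Sections 9.5 and 9.7 on who belongs to the PER, and the missing restriction in Section 9.7.2. An SAP cannot settle these without departing from one protocol statement.

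**Conclusion.** The point holds as a conflict within the protocol and a missing restriction on the primary rate. It does not show that the planned primary estimate is biased, because the prospective estimate is planned and can be reported.

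The possible effect is large at the size the protocol expects. Under the assumed 20 live births and true rates of 2% to 5%, two defect-triggered reports raise the expected proportion to between 5.5 and 2.7 times the true rate. At 100 live births and a 3% rate, two such reports give 4.9%, so the effect shrinks with size but does not vanish. These figures depend on assumed n, p0 and k. The upward direction does not depend on them, as long as the added reports exist because of a defect.

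**What to change.** - **Section 9.7.2:** state that the primary and secondary rates, their confidence intervals and the external comparison use prospective pregnancies only, as defined in Section 9.2.4.
- **Other sets:** present retrospective, literature and defect-triggered spontaneous reports, and the combined and pooled sets, as counts and line listings by source, with no rate, interval or test.
- **Section 9.1:** name the display that receives spontaneous and literature reports of defects.
- **Sections 9.5 and 9.7:** agree on whether known-outcome spontaneous and literature reports belong to the PER.
- **Sections 4.9, 9.2.4 and 9.7:** word the separation rule and the planned combinations so that both can be followed.

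Optionally, add one supportive prospective rate that includes non-enrolled prospective spontaneous reports, classified by whether the outcome was known when reported.

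The cost is wording and table shells, with no new data or contacts. The sponsor gives up the combined and pooled percentages.

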9.2 Setting

Subjects will be accepted from all countries where LOWER is being conducted. Physicians who are treating adult patients with lomitapide will be informed about the PER and invited to notify the CC of any patient who meets the eligibility criteria.

Confidential Page 20 of 54

To raise awareness of the PER amongst prescribers and patients, information about it will be disseminated through a variety of mechanisms which may include educational materials, labeling, and follow-up on spontaneous reports of pregnancy.

9.2.1 Patient Eligibility

Inclusion criteria are broad and exclusion criteria are limited in order to include a representative population of patients taking the product in usual clinical practice.

9.2.2 Inclusion Criteria

The eligibility criteria for patients enrolled in the PER are:

- Adult (≥18) pregnant females exposed to lomitapide at any time within 30 days prior to first day of the LMP or during pregnancy.
- Patients who have the ability to understand the requirements of the study.
- Patients who have provided written consent for participation.

A patient may first provide oral consent on a recorded line if she is enroling herself. The CC will then send the patient a consent form for signature, to be returned in a provided postage-paid envelope. Following completion of oral consent, collection of enrolment data will proceed. If a physician obtains informed consent, the physician will indicate to the CC that verbal consent was obtained. The physician will then be sent a consent form for completion by the patient at her next visit.

9.2.3 Exclusion Criteria

Patients who are unable or unwilling to provide written informed consent or assent are not eligible to participate in the PER.

9.2.4 Prospective and Retrospective Pregnancy Definitions

In order to reduce the bias that may occur when outcome information is known prior to enrolment, eligible women are advised to enrol in the PER as soon as their pregnancy is known, preferably in the first trimester before the condition of the foetus has been assessed through prenatal testing. In order to determine the impact of such a bias, pregnancy reports and outcomes will be classified as either prospective or retrospective and will be analysed separately.

Confidential Page 21 of 54

The criteria for prospective pregnancies are:

Prospective pregnancies will include patients who are enrolled after exposure to lomitapide but before the outcome of the pregnancy is known. An exception will be made that women who have undergone prenatal testing that could provide knowledge of the outcome of pregnancy will be considered as a prospective report if the outcome of the testing is normal.

Note: Because early prenatal testing is so prevalent, it may be difficult to achieve adequate numbers of prospectively identified patients if all pregnancies with prior prenatal testing are excluded from the prospective analysis. Therefore, the primary analysis includes pregnant women enroled prior to outcome but after a prenatal test as long as the test does not indicate an abnormality. However, this practice could potentially bias the results by lowering the overall risks of birth defects. To examine this possible source of bias, the analysis will also be conducted excluding the subgroup of women who reported negative prenatal testing at the time of enrolment.

All other patients will be counted as retrospective pregnancies.

The retrospective and prospective pregnancies will be collected in a similar fashion, but treated separately as part of any analyses or reports.

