9.3.1.1 Spontaneous Abortion/Miscarriage

The PER defines any loss of a foetus due to natural causes at less than 20 weeks gestation (with gestational age measured from the first day of the LMP) as a spontaneous abortion. If available, data from gross or pathological examination of the abortus or foetus will be evaluated for structural or chromosomal defects.

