9.7.1 Potential Biases

As reporting of pregnancies will be totally voluntary, it is possible that even in prospectively reported pregnancies, potential bias could exist. For example, high-risk pregnancies may be more likely to be reported.

The calculation of risk of birth defects will exclude foetal losses (spontaneous abortions, induced abortions, or foetal deaths) for which no birth defects have been detected as they may introduce a classification bias. It is unknown what percentage of these pregnancies consists of potentially normal outcomes or birth defects. The PER will attempt to obtain information on birth defects detected at the time of foetal loss. However, the reporting HCP may not know the defect status of the aborted foetus. Evaluating spontaneous pregnancy losses is problematic for a number of reasons. First, the number of pregnancy losses in the general population is not well established. Early losses generally occur frequently and losses decrease as pregnancy progresses. Collecting information on pregnancy losses is difficult in this voluntary PER when enrolment time or initial contact with PER cannot be regulated. Spontaneous losses are likely to occur before the pregnancy is recognized. Even if the pregnancy is recognized, it may not be reported to the PER if the spontaneous loss occurred prior to PER enrolment.

Every effort will be made to obtain the outcome of every reported pregnancy. However, enroled patients for whom pregnancy outcome information is unobtainable will be considered lost to follow-up. It is possible that outcomes from pregnancies lost to follow-up could differ from those with documented outcomes. Because of differences in follow-up and reporting patterns, it is currently not possible to assess with any certainty what impact the potential biases of the loss to follow-up may have on the analysis. However, efforts at comparing some of the

Confidential Page 35 of 54

characteristics of each group will be conducted in an attempt to address this potential source of bias.

As lomitapide is indicated for individuals 18 years and older, data from females who become pregnant under the age of 18 will not be included; however, the number of excluded pregnant females will be reported in study reports.

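### In the prospective group, enrolment at any gestational age biases the planned spontaneous-abortion percentage low, and no planned analysis accounts for entry time

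*Protocol*

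**What the plan says.** Eligibility (Section 9.2.2) covers "Adult (≥18) pregnant females exposed to lomitapide at any time within 30 days prior to first day of the LMP or during pregnancy", with no limit on gestational age at enrolment. Section 9.2.4 advises enrolment as soon as the pregnancy is known, "preferably in the first trimester before the condition of the foetus has been assessed through prenatal testing", but this is not a criterion. Prospective status depends on what is known at enrolment: "Prospective pregnancies will include patients who are enrolled after exposure to lomitapide but before the outcome of the pregnancy is known". Women with a normal prenatal test stay in this group. For the remainder, "All other patients will be counted as retrospective pregnancies".

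Section 9.3.1 makes spontaneous abortion one of four mutually exclusive pregnancy outcomes, and Section 9.3.1.1 defines it as "any loss of a foetus due to natural causes at less than 20 weeks gestation", counted from LMP.

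Section 9.7 states "Data will be presented for all patients enroled in the PER", adds separate prospective and retrospective analyses, and continues: "Data will be presented using descriptive statistics using number and percent for categorical endpoints". Complete specifications and table shells are left to the SAP. The only strata the protocol names (Section 9.7.2) are for birth defects: earliest trimester of exposure, maternal age and other maternal risk factors.

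Section 9.7.1 says that losses are most frequent early, that enrolment time cannot be regulated, and that even when a pregnancy is recognised, "it may not be reported to the PER if the spontaneous loss occurred prior to PER enrolment".

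**The concern.** A percentage of enrolled pregnancies estimates the risk of spontaneous abortion only if women are followed from the start of the risk period. Here follow-up starts at whatever week a woman enrols. Losses before that week are not seen in the prospective group, and a woman enrolled at 24 weeks adds to the denominator although she can no longer contribute to the numerator. The result depends on when women happen to enrol as well as on any effect of lomitapide.

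Section 8 sets out to evaluate the outcomes of pregnancy, and Section 9.9.1 says broadly that outcomes data will be compared with published rates. A low crude percentage in an annual report could be read as reassurance when it mainly shows late enrolment.

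For two other biases the protocol does plan a response: a sensitivity analysis for prior normal prenatal testing (9.2.4) and a comparison of characteristics for loss to follow-up (9.7.1). Delayed entry is named and left without one.

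**Working it through.** The protocol states no spontaneous-abortion rate, entry distribution or sample size, so there is no figure to reproduce. What follows illustrates direction and rough size under assumed inputs.

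**From the protocol:** event window below 20 weeks from LMP (9.3.1.1); entry at any week (9.2.2, 9.2.4); summary by number and percent (9.7).

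**Assumed:** total risk R from week 5 to the end of week 19 of 15% (range 10–20%); weekly hazard falling by a factor d of 0.85 per week (range 0.75–0.85); entry weeks spread evenly over 6–12, 8–20 or 6–36.

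**Step 1, hazard.** h(w) = c × d^(w−5) for w = 5 to 19, with c chosen so that the product of (1 − h(w)) equals 1 − R. For R = 15% and d = 0.85, c = 0.0265.

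**Step 2, risk still observable.** For a woman entering at the start of week e it is 1 − S(20)/S(e), where S(e) is the proportion of pregnancies continuing to week e and S(20) = 0.85. Results use unrounded values.

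| Entry week | S(e) | Observable risk |
|---|---|---|
| 6 | 0.9735 | 12.7% |
| 8 | 0.9333 | 8.9% |
| 10 | 0.9055 | 6.1% |
| 12 | 0.8859 | 4.0% |
| 16 | 0.8621 | 1.4% |
| 20 or later | – | 0% |

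**Step 3, crude prospective percentage.** This is the average of Step 2 over the entry weeks of enrolled women.

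| Entry weeks | R = 15%, d = 0.85 | Range over R = 10–20%, d = 0.75–0.85 |
|---|---|---|
| 6–12 | 7.8% | 3.7–10.6% |
| 8–20 | 3.3% | 1.2–4.4% |
| 6–36 | 2.1% | 0.9–2.9% |

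In each scenario the percentage lies below the R assumed for it.

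**Step 4, combined set.** Take the prospective part as 3.3% (entry weeks 8–20) and let a share s of all reports be retrospective, half of them spontaneous abortions (both assumed). The combined percentage is (1 − s) × 3.3 + s × 50.
- s = 20%: 2.6 + 10 = 12.6%
- s = 30%: 2.3 + 15 = 17.3%
- s = 40%: 2.0 + 20 = 22.0%

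The first is below the assumed 15% and the other two are above it.

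**Step 5, restricting the denominator.** With entry over weeks 6–36, 14 of the 31 entry weeks fall before week 20. Dropping the rest gives 2.12 × 31/14 = 4.7%. This removes women who cannot have the event. It does not recover the 15%, so the result must also be shown by entry week.

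**Step 6, delayed-entry life table.** In a simulation of 400,000 pregnancies (R = 15%, d = 0.85, entry weeks 6–20), the crude percentage was 4.6%, the true risk from week 6 was 12.7% and the delayed-entry product-limit estimate was 12.8%. In small samples with the same entry weeks, the root mean squared error around 12.7% was about 20 points for the life table against 10 for the crude percentage with 10 pregnancies, and 11–12 against 9 with 50. With 10 pregnancies, about 62% of runs gave an estimate of zero.

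**The case against.** The strongest reply has four parts.

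1. **The protocol discloses the problem and acts on entry time.** Section 9.7.1 calls spontaneous losses problematic to evaluate, and early reporting is pursued through advice (9.2.4), outreach (9.3.4.1.1) and enrolment instructions (9.3.4.1.2). This stands. A reader might infer that the bias was overlooked, and the text does not support that. What is missing is an analysis to match the admission.

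2. **Details belong to the SAP, which is not shown.** Section 9.7 gives no explicit denominator for spontaneous abortion and excludes no further method, so the SAP may already handle entry time. This limits the weight of the point. It does not remove it, because the summary the protocol does state would mislead if carried out as written.

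3. **The direction is not general.** A reader might infer that the percentage among all enrolled women is biased low. That does not follow: retrospective reports can be made after the outcome is known, and Step 4 shows the combined figure on either side of the assumed risk. Section 9.7.1 also warns that high-risk pregnancies may be over-reported, even prospectively. That is a separate bias of unknown size and cannot be relied on to cancel this one.

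4. **A required life table could do more harm than good.** Few pregnancies are expected (Section 7), and at 10 or 50 pregnancies the delayed-entry estimate had the larger total error in Step 6. This stands and argues against making it the main analysis.

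Two further inferences should be resisted. The protocol plans no comparison between countries with patient reports and countries restricted to HCPs, so distortion of such a comparison is not a planned harm. The chi-square comparison in Section 9.7.2 concerns birth defects, whose primary proportion uses live births as denominator; nothing here tests that analysis.

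**Conclusion.** The point holds for the prospective group. Entry is open at any gestational age, the event is possible only before 20 weeks, and the stated summary is number and percent, so delayed entry biases the spontaneous-abortion percentage low. The direction of this component follows from the definitions together with the protocol's own statement that losses are most frequent early.

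The size depends wholly on assumed risk, hazard shape and entry weeks. Across the scenarios shown, the crude percentage runs from 0.9% to 10.6% for assumed risks of 10–20%. In the combined prospective and retrospective set the direction is not fixed, and that percentage cannot be read as a risk.

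Spontaneous abortion is not the primary outcome and the limitation is partly disclosed, so this is an inexpensive improvement that should be made. It is not a fault in the main analysis.

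**What to change.** In Section 9.7:

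- Use as the denominator for the spontaneous-abortion proportion only prospective pregnancies enrolled before 20 weeks from LMP.
- Report prospective pregnancy outcomes by gestational week at enrolment, derived from LMP and date of initial contact, both collected under Section 9.4.
- State that the crude percentage is not to be compared with published loss rates.
- Optionally, if numbers allow, add a delayed-entry life table on gestational age as a supportive analysis. Treat induced abortion as a competing event, since censoring at it would assume independence from the risk of spontaneous loss.

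The cost is a few sentences and one table, with no new data collection. The downside is a smaller denominator and a wider interval.
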